#### **Exclusion Criteria**

- Any contraindication to receiving regional anesthesia. This may include infection at the site of injection, allergy to local anesthetic, or pre-existing nerve injury.
- Patients undergoing hamstring graft or allograft for ACL
- Pre-existing infection at the site of injury
- Patients on chronic opioid treatments
- Pre-existing sensory or motor deficit in operative extremity
- Patients having a revision of previous ACL reconstruction
- Pregnant and/or lactating women
- Weighs less than 40kg

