#### **Baseline and Randomization**

After consenting and confirmation of meeting eligibility criteria, the participant will undergo the procedure as scheduled and as standard of care. The participant will be

randomized before they are anesthetized, as the block will be prepared and placed prior to the start of surgery.

If randomized to ACB-Only (Group A) the participant will receive the ACB block first. The injection site is prepared with a sterile solution, an injection of lidocaine is given to numb the area, then using ultrasound guidance a needle is inserted into the adductor canal at the mid-thigh where a catheter is placed to administer the long-acting anesthetic. Next, to maintain the blind, the participant will receive a skin wheal with lidocaine at the same location as Group B has the iPACK block placed.

Table 5. Post-Op Follow Up Assessments			
Outcome Measure	Instrument	Collected	
Pain Rating	Average pain, most pain, least pain from 0-10 POD Days 0-3		
Opioid Consumption	Number of pills taken in time period POD Days 0-3		
Physical Therapy	Range of Motion and terminal knee extension	Postoperative Visit 1 and 2	
Adverse Events	Adverse Events	Throughout enrollment	

If randomized to ACB + iPACK (Group B) the participant will be administered the ACB first as stated above and the iPACK block second. The iPACK block will be placed at the posterior part of the knee. The area will be numbed first using lidocaine, then using ultrasound guidance, a needle will be inserted in the popliteal fossa between the popliteal artery and the capsule of the knee.

Table 4. Baseline and Intraoperative Assessments		
Demographics		
Baseline		
Pre-op meds including opioids in past 24 hours		
Randomization		
Anesthesia intra-op data		
Surgical techniques		
Adverse Events		

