### 11.0 Data Management

- The study will be a double-blinded randomized controlled trial of participants undergoing ACL reconstruction at one academic medical center. Although the anesthesiologist administering the block will not be blinded, the surgeons, participants, and study statistician will be blinded to treatment assignment. Participants will be randomized to receive either ACB or ACB + iPACK block. We will use stratified randomization, stratifying on biologic sex, to ensure similar distributions of male/female participants in each treatment arm the same.
- The primary outcomes of interest are participant reported postoperative pain over time and quadricep strength based on the leg raise and knee extension test. Postoperative VAS pain score reported as average, worst, and least pain will be collected on post-op day 0 (after 12pm), 1 (prior to 12 pm and after 12 pm), and 2 (before 12 pm). The association between postoperative pain with block type will be evaluated using a series of linear mixed models evaluating average pain, worst pain, and least pain as dependent variables. Models will include fixed effects for preoperative pain score, block type, postoperative time, and the interaction between block type and post-operative time and a random subject effect to account for correlation between pain scores collected on the same subject over time. Model assumptions will be checked graphically, and transformations will be considered as needed. The difference in patient reported pain between block type by post-operative time and pain score type will be evaluated using a series of linear contrasts. A similar study

by Amer  $(2018)^1$  comparing combined Adductor Canal and iPACK Blocks versus combined Adductor Canal and Periarticular Injection blocks for pain management in ACL Reconstruction Surgery found a difference in VAS pain scores of 1.5 between 0 to 8 hours post-op and standard deviation in VAS pain of 2.5 units. A sample size of n=35 participants per treatment arm (70 total) with at least 3 measures of pain provides 80% power to detect a difference in pain score of 2 units at significance level  $\alpha=0.004$  (Bonferroni corrected for 4 comparisons) and assuming a compound symmetric covariance structure with a conservative standard deviation = 3.0 and correlation within subject is  $\rho=0.33$ . We will enroll 41 participants (82 total) in each arm to allow for up to 20% attrition.

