- Secondary outcomes include cumulative post-operative opiate consumption over time (POD 0 pm, 1 am/pm, and 2 am), and difference in range of motion between surgical and non-surgical leg at first clinic visit (7-21 days post-op) and 6 weeks PO. Associations between these secondary outcomes with block type will be evaluated using a linear mixed approach. Similar to the primary outcome, models will include fixed effects for type, time, and the interaction between block type and time. The model for cumulative opiate consumption will also include a fixed effect for intra-operative opiates received and the model for range of motion will include a fixed effect for pre-operative difference in range of motion between surgical and non-surgical leg.
- All data will be kept on a password protected MUSC server and in a REDCap database. All paper data sheets will be kept in a locked cabinet, in a locked office that only IRB approved study team members have access to. Participants will be given a study ID number that will be used to identify them throughout the study.

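### The cumulative opioid model has no pre-randomisation covariate, although the plan adjusts its other models for a baseline value and records opioid use in the 24 hours before surgery: a modest loss of precision, not a bias

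*Combined protocol and SAP*

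**What the plan says.** Section 11.0 gives the terms shared by the secondary-outcome models: "models will include fixed effects for type, time, and the interaction between block type and time". It then adds one covariate to each. For opioids: "The model for cumulative opiate consumption will also include a fixed effect for intra-operative opiates received". For range of motion, the addition is the preoperative difference between the two legs.

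The primary pain models in the same section do carry a baseline value: "Models will include fixed effects for preoperative pain score, block type, postoperative time".

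Table 4, under Baseline and Randomization in section 10.0, includes the item "Pre-op meds including opioids in past 24 hours". No model in section 11.0 uses it. The exclusion criteria in section 5.0 remove "Patients on chronic opioid treatments" but do not mention short-term use.

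On timing, section 10.0 says participants are "randomized before they are anesthetized, as the block will be prepared and placed prior to the start of surgery". On balance, section 11.0 says: "We will use stratified randomization, stratifying on biologic sex".

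**The concern.** Of the three kinds of outcome modelled, only opioid consumption has no baseline term. Its single added covariate is measured during surgery, after randomisation and after the block, so it cannot do the work of a baseline covariate. No reason is given for treating this outcome differently.

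What is at stake is precision. Opioid consumption is named beside pain in the section 1.0 hypothesis, yet no power calculation covers it. If preoperative pain or recent opioid use predicts later opioid use, leaving it out gives a wider confidence interval for the block effect than the trial's own data would allow. Randomisation is stratified by sex only, so the design does not balance either variable beyond what chance provides.

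**Working it through.** **1. The plan's own figure.** The documents give no sample size, standard deviation or power for opioid use. The only calculation is for pain, and it is needed here just for the number analysed. Section 11.0 gives a difference of 2, SD 3.0, within-subject correlation 0.33, 3 measures, alpha 0.004 and 80% power. Sidedness is not stated; two-sided reproduces the figure.

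- SD of the mean of 3 measures: 3.0 × √((1 + 2 × 0.33)/3) = 2.232.
- n per arm: 2 × (2.878 + 0.842)² × 2.232²/2² ≈ 34.5, so 35 per arm and N = 70, as stated.

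**2. Which models hold a baseline covariate (section 11.0).**

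| Model | Covariate beyond block, time and interaction | Before randomisation? |
|---|---|---|
| Pain | Preoperative pain score | Yes by its role; timing of collection not stated |
| Range of motion | Preoperative leg difference | Yes by its role |
| Cumulative opioids | Intra-operative opiates | No |

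**3. Effect of adding two covariates.** Let R² be the share of between-participant variance in opioid use that the two covariates jointly explain beyond terms already in the model. The documents do not give it, so the values below are assumptions. With k added covariates, a usual approximation for the expected variance ratio (added versus not added) in a two-arm comparison is

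(1 − R²) × (N − 3)/(N − 3 − k).

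With N = 70 and k = 2 the second factor is 67/65 = 1.0308. The SE ratio is the square root of the variance ratio, and the net gain in participants is 70/(variance ratio) − 70. The last column assumes that power without the covariates is 80% at two-sided 0.05. It is Φ((0.842 + 1.960)/SE ratio − 1.960).

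| Assumed R² | Variance ratio | SE ratio | Net participants | Power if 80% without |
|---|---|---|---|---|
| 0 | 1.031 | 1.015 | −2.1 | 78.8% |
| 0.01 | 1.020 | 1.010 | −1.4 | 79.2% |
| 0.04 | 0.990 | 0.995 | +0.7 | 80.4% |
| 0.09 | 0.938 | 0.969 | +4.6 | 82.5% |
| 0.16 | 0.866 | 0.931 | +10.8 | 85.3% |

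**4. Break-even.** The variance ratio equals 1 when R² = 1 − 65/67 = 0.030, a joint correlation of about √0.030 = 0.17. Below that, adding both terms costs slightly more than it returns. With one term only (k = 1), break-even is R² = 1 − 66/67 = 0.015.

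**The case against.** The strongest reply is that nothing is wrong. Leaving a prognostic covariate out of a randomised comparison is valid, the model is specified in advance, and nothing in the documents requires either term. That stands, and it is why this is a point about efficiency only.

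The opioid sentence also likens the secondary models to the primary one, which could be read as carrying preoperative pain across. The list that follows does not name it, so at best the text is ambiguous. On either reading, opioid use in the previous 24 hours stays out.

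Recent opioid use may hardly vary. Chronic users are excluded, and the documents do not say how many short-term users to expect. This stands, and the fix allows for it.

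Some stronger readings are tempting but unsupported:

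- *The estimate is biased, or chance imbalance goes uncorrected into it.* Randomisation protects the comparison, and the ordinary standard error already reflects chance imbalance. Counting imbalance as a further harm counts the precision argument twice.
- *The gain is free and worth 3 to 13 participants.* That is 70/(1 − R²) − 70 at R² = 0.04 and 0.16 (2.9 and 13.3), which ignores the two degrees of freedom. The net figures are about 1 and 11.
- *Opioid use is the main secondary endpoint.* It is listed first, but the documents do not rank it above range of motion.
- *The preoperative pain score is already held and certainly precedes the block.* Section 11.0 relies on it, but Table 4 has only a generic baseline line and the Follow-Up section describes postoperative scores only. Collection before randomisation is inferred, not stated.

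**Conclusion.** The omission is plain from section 11.0: the cumulative opioid model has no covariate measured before randomisation, in contrast to the plan's other models. It is a modest efficiency loss on a secondary endpoint and does not threaten validity.

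The likely size runs from nothing to about a 7% smaller standard error for R² up to 0.16, with a worst case of about 1.5% the other way. It rests on an assumed R², counted beyond intra-operative opiates while that term stays in the model; on 70 analysed participants; and on treating the block contrast as a participant-level comparison. The documents support the availability of the 24-hour opioid item directly and that of the pain score by inference.

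Adjusting for intra-operative opiates, which the block could itself change, is a different question about what the model estimates. Adding baseline terms neither settles it nor depends on it.

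**What to change.** In the secondary-outcome paragraph of section 11.0, add to the cumulative opioid model:

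1. a fixed effect for the preoperative pain score, as in the pain models, stated to be recorded before randomisation and the block; and
2. a fixed effect for any opioid in the 24 hours before surgery (yes/no, from the Table 4 item), kept only if a check blinded to arm shows that it varies among participants. Write down beforehand what counts as enough variation.

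Make the change before unblinding, so that the choice of covariates cannot follow the results.

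The cost is a sentence or two and up to two degrees of freedom. No new data are needed for the opioid item. For the pain score, a line in Table 4 should say when it is taken; the primary pain models need that in any case. The intra-operative opiate term should be dealt with separately.

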### 1.0 Objectives / Specific Aims

We hypothesize that participants receiving the ACB-iPACK intervention will have lower subjective pain scores and lower total opioid consumption in the initial 72-hours of the postoperative window and increased range of motion at subsequent follow up visits with their surgeon.

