# 4.0 Study Endpoints (if applicable)

- The primary endpoint will measure subjective pain scores as 12-hour intervals during the first 72 hours of the postoperative window as collected by a study team member.
- The secondary endpoints will measure total postoperative opioid consumption through postoperative day 2, as well as measure the range of motion and terminal knee extension of participants at postoperative follow-up visits.

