## 10.0 Study Design / Methods

This study will be a prospective, single-center, single-blind randomized controlled trial. Participants will be randomized by using a stratified randomization technique, stratified by sex into two groups:

- 1) continuous adductor canal block alone (ACB Only) or
- 2) continuous adductor canal block with iPACK block (ACB + iPACK).

Preoperative: Adult participants and pediatric patients >70kg will receive 1g Tylenol and 1-2mg midazolam and up to 20mcg of dexmedetomidine for preprocedure anxiolysis. Patients between 12 and 18 years old will receive Tylenol with a dose based on weight (Table 1), and 1-2mg midazolam and up to 20mcg of dexmedetomidine.

Table 1. Tylenol Dosage Based on Weight for Pediatrics		
Weight	Dosage	
≥70kg	1,000mg	
45-70kg	650mg	
<45kg	500mg	

All participants will receive the continuous adductor canal block which consists of 20cc of 0.25% plain ropivacaine and will be given followed by placement of an OnQ pump infusing 0.2% ropivacaine at 6cc/hr. (4cc/hr. for participants less than 60Kg).

Those who are randomized to the ABC + iPACK group will receive an additional block consisting of 20cc of 0.25% Ropivacaine placed in the popliteal fossa between the popliteal artery and the posterior aspect of the capsule of the knee joint.

Participants randomized to the ACB-only group will receive a skin wheal at the same site where the iPACK block would have been placed in an effort to maintain the blind.

Perioperative: Participants will be appropriately sedated as per clinical care.

Postoperative: Participants will be given 0.2mg hydromorphone every 8 minutes as needed for pain, and 5mg of oxycodone may be administered adjunctively as needed if pan scores remain elevated after intravenous hydromorphone

Post-discharge: Participants will be instructed to schedule two post-operative follow up appointments with their surgeon as well as physical therapy. They will also be prescribed the following medication regimen after discharge:

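### The only planned opioid model adjusts for intra-operative opioids, a post-randomisation variable, so its block contrasts need not be the total effect of adding iPACK on post-operative opioid use

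*Combined protocol and SAP*

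**What the plan says.** Section 11.0 (Data Management) plans a linear mixed model for cumulative post-operative opioid use, with block type, time and their interaction. It adds one further term: "The model for cumulative opiate consumption will also include a fixed effect for intra-operative opiates received". No opioid model without that term is planned, and no reason for it is given.

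The order of events is fixed under Baseline and Randomization. Participants are "randomized before they are anesthetized, as the block will be prepared and placed prior to the start of surgery". Opioids given during surgery therefore come after assignment and after the block.

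No intra-operative opioid regimen is stated. The perioperative line in section 10.0 reads only: "Participants will be appropriately sedated as per clinical care".

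The question is framed as a total effect. Section 1.0 hypothesises "lower total opioid consumption in the initial 72-hours of the postoperative window", and section 4.0 lists "total postoperative opioid consumption through postoperative day 2" among the secondary endpoints.

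The other two models in section 11.0 use pre-operative covariates. For pain: "Models will include fixed effects for preoperative pain score, block type, postoperative time". For range of motion: a "fixed effect for pre-operative difference in range of motion between surgical and non-surgical leg".

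**The concern.** Randomisation makes the arms comparable in everything that precedes it. A covariate measured afterwards does not share that protection, because treatment may already have changed it. An analgesic block placed before incision could plausibly alter how much opioid is given during surgery, and nothing in the documents fixes that amount.

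If it does, and if intra-operative opioids are associated with later use, conditioning on them removes part of the comparison that the trial set out to make. The documents define no direct-effect estimand that would justify this. With only the adjusted model planned, a reader of the results could not tell whether the reported contrast is the effect on total post-operative opioid use, which is part of the trial's hypothesis.

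**Working it through.** **Plan's own figure.** The documents give no SD, effect size or power for opioid use. The only design figure is 35 per arm for pain. It reproduces: the SD of a mean of three measures is 3.0 × √((1 + 2 × 0.33)/3) = 2.232, and at two-sided 0.004 a difference of 2 needs 35 per arm (power 80.8%, normal approximation). I borrow only the 35.

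**Identity.** Let *a* be the effect of adding iPACK on intra-operative opioids and *g* the model's fitted within-arm slope of post-operative on intra-operative opioids. Then

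total effect − adjusted contrast = *a* × *g*.

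The gap is zero only if *a* = 0 or *g* = 0. The covariate does not vary over time and has no interaction with time in the plan, so the same shift applies to every block contrast.

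**Assumed inputs (none is in the documents).** 35 per arm; four windows, as listed for this outcome in section 11.0; within-arm SD of intra-operative opioids and of the final total both 1; true benefit 0.5 SD; two-sided 5% test; a random subject intercept, carried over from the pain model. Let *d* be the reduction in intra-operative opioids and *r* their within-arm correlation with the final total.

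- Middle case: *d* = 0.3, *r* = 0.3, *d* × *r* = 0.09.
- Upper case: *d* = 0.5, *r* = 0.5, *d* × *r* = 0.25.

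**Estimate from the planned model.** With a random intercept, the single shared slope is the plain mean of the four cumulative slopes, so the shift is *d* × *r* × that mean share:

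| Which windows intra-operative opioids predict | Mean share | Middle: shift → estimate | Upper: shift → estimate |
|---|---|---|---|
| First only | 1.000 | 0.090 → 0.41 | 0.250 → 0.25 |
| Falling 4:3:2:1 | 0.750 | 0.068 → 0.43 | 0.188 → 0.31 |
| Equal | 0.625 | 0.056 → 0.44 | 0.156 → 0.34 |
| Last only | 0.250 | 0.023 → 0.48 | 0.063 → 0.44 |

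For example, the equal row has (0.25 + 0.50 + 0.75 + 1.00)/4 = 0.625, and 0.25 × 0.625 = 0.156. A regression on the final total alone gives the first row.

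**Scale.** The unadjusted standard error is √(2/35) = 0.239 SD. The middle-case shift is 0.023/0.239 ≈ 0.1 to 0.09/0.239 ≈ 0.4 of a standard error.

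**No true total effect.** Here the adjusted contrast equals +*d* × *r* × share. For the single-outcome upper case:

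- Standard error = 0.239 × √(1 − 0.25) × √(1 + 0.25/4) = 0.213; the last factor reflects the arm difference in the covariate.
- Ratio = 0.25/0.213 ≈ 1.17.
- Rejection: 21.0% toward more opioid use with iPACK and 0.1% toward benefit.

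If all windows are predicted equally, the upper case rejects 11% to 12%. The middle case rejects 5% to 7%; in the single-outcome version this is about 5.8% toward harm and 1.0% toward benefit.

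**Price of dropping the covariate when *a* = 0.** The standard error widens by at most 1/√(1 − *r*²): 1.021, 1.048 and 1.155 at *r* = 0.2, 0.3 and 0.5. At *r* = 0.5 the adjusted standard error is 0.239 × √0.75 = 0.207. Power for 0.5 SD (noncentral t) is then 66% with the covariate and 54% without it.

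**The case against.** **The bias is possible, not shown.** This stands. Two conditions must both hold, and the documents establish neither. Both arms receive the same continuous adductor canal block, so only the increment from iPACK matters. The upper case needs that increment alone to cut intra-operative opioids by half an SD. In the middle case the shift is well under one standard error and rejection stays near nominal.

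**The covariate adds precision.** It can, if it is prognostic and the block leaves it unchanged. But the plan cannot know that in advance, and precision does not help if the contrast is no longer the stated effect.

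**It estimates a direct effect.** Not reliably. Suppose, by assumption, that an unmeasured cause has loading 0.5 on both intra- and post-operative use, with a direct effect of −0.30 and *a* = −0.50. The adjusted contrast becomes −0.30 − 0.25 × (−0.50) = −0.175, which is not the direct effect.

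**The window count is a choice.** Table 6 collects seven windows. Using seven, the upper-case shifts become 0.25, 0.18, 0.14 and 0.04 SD, and the conclusion is unchanged.

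**Stronger readings that the documents do not support.**
- A reader might infer that the opioid result will be biased, or biased in a known direction. No figure in the documents supports either.
- A reader might take the 21% as false claims of benefit. Under the assumed signs it is almost entirely false harm.
- A reader might infer that an unblinded anesthesiologist will dose by arm. The documents do not say who gives intra-operative opioids, and the point rests on timing alone.

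**Conclusion.** The point holds in conditional form. The covariate is measured after randomisation and after the block, the aim is a total effect, and the only planned opioid model conditions on that covariate. If adding iPACK changes intra-operative opioids and these predict later use, the adjusted contrasts are not the total effect; otherwise there is no systematic shift.

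Under the assumed inputs and a random intercept, the shift is 0.02 to 0.09 SD in the middle case and 0.06 to 0.25 SD in the upper case. With iPACK lowering intra-operative use and a positive association, a real benefit is understated. A negative association, or a block that raises intra-operative use, would reverse the direction.

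One secondary outcome is affected. The pain and range-of-motion models adjust for pre-operative values and are not. The plan should be changed because the remedy is cheap, not because serious bias has been demonstrated.

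**What to change.** In the secondary-outcome text of section 11.0:

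1. Make the main model for cumulative post-operative opioid use free of post-randomisation covariates.
2. Adjust only for pre-randomisation variables already collected: sex, which is the stratification factor, and pre-operative opioids in the past 24 hours (Table 4) if they vary enough. They may not, because section 5.0 excludes patients on chronic opioid treatment.
3. Report intra-operative opioids by arm as a separate outcome. Table 4 already lists intra-operative anesthesia data. This shows readers whether the first condition holds.
4. Keep the currently planned model as a labelled sensitivity analysis.

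This changes SAP wording only and needs no new data. It should be settled before unblinding, since dropping the covariate at reporting would be post hoc. The real cost is precision if intra-operative opioids are prognostic and unaffected by the block: a standard error wider by at most about 2%, 5% or 15% at correlation 0.2, 0.3 or 0.5. Any prognostic value in the pre-randomisation covariates would offset part of that.
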